Appendix C: 5-D Itch Scale

This is a representation of the content of the instrument to be used. Please refer to the Study Reference Manual for the instrument to be administered to patients and instructions.

1. DURATION:	During the last 2 weeks, how many hours a day have you been itching?				
	Less than 6 hrs/day	6-12 hrs/day	12-18 hrs/day	18-23 hrs/day	All day
2. DEGREE:	Please rate the intensity of your itching over the past 2 weeks				
	Not present	Mild	Moderate	Severe	Unbearable
3. DIRECTION:	Over the past 2 weeks has your itching gotten better or worse compared to the previous month?				
	Completely resolved	Much better, but still present	Little bit better, but still present	Unchanged	Getting Worse
4. DISABILITY:	Rate the impact of your itching on the following activities over the last 2 weeks				
	Never affects sleep	Occasionally delays falling asleep	Frequently delays falling asleep	Delays falling asleep and occasionally wakes me up at night	Delays falling asleep and frequently wakes me up at night
Sleep					
	Never affects this activity	Rarely affects this activity	Occasionally affects this activity	Frequently affects this activity	Always affects this activity
N/A					
Leisure/Social					
Housework/Errands					
Work/School					
5. DISTRIBUTION:	Mark whether itching has been present in the following parts of your body over the last 2 weeks. If a body part is not listed, choose the one that is closest anatomically.				
	Head/Scalp		Soles		
	Face		Palms		
	Chest		Tops of Hands/Fingers		
	Abdomen		Forearms		
	Back		Upper Arms		
	Buttocks		Points of Contact w/ Clothing (e.g. waistband, undergarment)		
	Thighs		Groin		
	Lower legs				
Tops of Feet/Toes					

Date Completed:								
 D	 D	 M	 M	 M	 Y	 Y	 Y	 Y

Time:		
 : 	 AM	 PM

SUBJECT INITIALS		
First	Middle	Last
		

Statistical Analysis Plan (SAP)

The scores of each of the five domains are achieved separately and then summed together to obtain a total 5-D Itch score. 5-D Itch scores can potentially range between 5 (no pruritus) and 25 (most severe pruritus)².

Single-item domain scores (duration, degree and direction) are equal to the value indicated below the response choice (range 1–5)². The disability domain includes four items that assess the impact of itching on daily activities: sleep, leisure/social activities, housework/errands and work/school. The score for the disability domain is achieved by taking the highest score on any of the four items. For the distribution domain, the number of affected body parts is tallied (potential sum 0– 16) and the sum is sorted into five scoring bins: sum of 0–2 = score of 1, sum of 3–5 = score of 2, sum of 6–10 = score of 3, sum of 11–13 = score of 4, and sum of 14–16 = score of 5.

Total 5-D Itch score = duration score (single item) + degree score (single item) + duration score (single item) + maximum (4 disability items) + category score based on sum of affected body parts.

Statistical Analysis Plan (SAP)

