6.5.1.2 Skindex-10 Scale

Developed specifically for uremic pruritus, the Skindex-10 Scale ([Appendix 3, Section 14.3](#)) is an instrument for measurement of quality of life that correlates with both itch intensity as well as other instruments evaluating quality of life in patients with uremic pruritus [[Mathur 2010](#)]. Patients are asked to fill in 1 of 7 circles numbered from 0 (labeled with the anchor phrase “never bothered”) to 6 (labeled as “always bothered”) for each of the 10 questions. The total score is the sum of the numeric value of each answered question. The total score is subdivided into 3 domain scores, which are sums of the scores of the following questions: disease domain (questions 1 to 3), mood/emotional distress domain (questions 4 to 6), and social functioning domain (questions 7 to 10).

6.5.1.3 5-D Itch Scale

The 5-D Itch Scale was developed as a brief, but multidimensional questionnaire designed to be useful as an outcome measure in clinical trials. The 5 dimensions of itch assessed are degree, duration, direction, disability, and distribution ([Appendix 4, Section 14.4](#)). The scale has been validated in patients with chronic pruritus and has been shown to be sensitive to changes in pruritus over time [[Elman 2010](#)].

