Weekly Mean Worst Itching Intensity NRS score	The weekly mean of the 24-hour Worst Itching Intensity NRS score will be defined as the sum of the daily Worst Itching Intensity NRS score reported during a specific week during the Treatment period (eg, Days 1 to 7, Days 8 to 14, Days 15 to 21, etc.) divided by the number of non-missing scores for that week. If there are <4 non-missing daily worst itching scores in a specific week, the corresponding weekly mean worst itching score will be set to missing.
Skindex-10	
Total Scores	Patients will be asked to fill in 1 of 7 circles numbered from 0 (labeled with the anchor phrase “never bothered”) to 6 (labeled as “always bothered”) for each of 10 questions. The total score is the sum of the numeric value of each answered question. For more details see Appendix B.
5-D Itch	
Total Score	Total 5-D Itch score = duration score (single item) + degree score (single item) + duration score (single item) + maximum disability (4 disability items) + category score based on sum of affected body parts. 5-D Itch scores can potentially range between 5 (no pruritus) and 25 (most severe pruritus). For more details see Appendix C

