8.6.3 Analysis of secondary efficacy endpoint(s)

The key secondary efficacy endpoints are:

- Change from baseline in itch-related quality of life at the end of Week 12, as assessed by the total Skindex-10 scale score;
- Change from baseline in itch-related quality of life at the end of Week 12, as assessed by the total 5-D Itch scale score;
- Proportion of patients achieving an improvement from baseline ≥ 3 points with respect to the weekly mean of the daily 24-hour Worst Itching Intensity NRS score at Week 12 of the Treatment period.

The Skindex-10 scale total score and the 5-D Itch total scale score will be analyzed using MMRM that will contain treatment, week, and treatment-by-week interaction as fixed effects; baseline score and renal disease status as covariates. Repeated measures will include values that reflect the Skindex-10 and 5-D total score at the end of weeks 4, 8, 10, and 12. The total score derivation for Skindex-10 and 5-D Itch scale detailed in [Appendix B](#) and [Appendix C](#) respectively.

The baseline value will be defined as the value of the Skindex-10 or 5-D Itch total score collected on Day 1 prior to randomization. Missing Skindex-10 Itch scale and 5-D Itch scale

Statistical Analysis Plan (SAP)

total scores will be imputed in a similar fashion as the primary endpoint for the MMRM analyses using the MI approach assuming data is missing at random. The mean treatment difference between each CR845 dose and placebo, and between all CR845 doses combined and placebo will be estimated as the simple contrast in the treatment effect at Treatment period week 12.

Descriptive statistics will be provided for the observed value and change from baseline at week 12 by treatment group for Skindex-10 scale and the 5-D Itch total scores. The adjusted LS means and SE from the model will be presented for each treatment group. The LS means estimate for the difference, standard error, 95% CI, and p-value will be presented. The analysis will be conducted using the Full Analysis Set.

An unstructured covariance matrix structure will be used to model the within patient errors. If there are convergence issues, other structures that require fewer parameters will be applied in the following order: 1) heterogeneous Toeplitz, 2) autoregressive, 3) compound symmetry until convergence is attained. The Kenward-Roger approximation will be used to estimate the denominator degrees of freedom.

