- Change from baseline in itch-related quality of life at each scheduled post baseline week of the Treatment period, as assessed by the total score of the 5-D itch scale. Treatment differences between each CR845 dose group and placebo at each post baseline time points will be evaluated and presented (except week 12) using the MMRM fitted for the secondary efficacy analysis [section 8.6.3](#).
- The proportion of patients who either rate the degree of itching intensity as 'Not Present' or the direction of itching as 'Completely Resolved' over the past 2 weeks from the 5-D Itch Scale will be calculated at Week 12 and end of treatment. Treatment differences will be compared using a logistic regression model with terms for treatment group, baseline 5-D Itch Total Score and renal disease status. In addition, pairwise treatment differences will be tested using the Cochran-Mantel-Haenszel test, adjusting for strata (i.e renal disease status). An exact test of whether the common odds ratio across strata equals 1 will be used if the observed count in a particular cell is small (ie, <5).
- The proportion of patients with itching present at each body part will be presented at Week 12 and end of treatment along with the shift from baseline (Present or Not Present combinations). The presence of itching at each body part at end of treatment will be compared between treatments adjusting for strata (i.e renal disease status) and presence of itch at baseline (Present/Not Present). An exact test of whether the

Statistical Analysis Plan (SAP)

common odds ratio across strata equals 1 will be performed.

- Change from baseline in itch-related quality-of-life at each week of the Treatment period, as assessed by the total score of the Skindex-10 Scale. Treatment differences between each CR845 dose group and placebo at each scheduled post baseline time points will be evaluated and presented (except week 12) using the same MMRM fitted for the secondary efficacy analysis [section 8.6.3](#).

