- The total Skindex-10 score is subdivided into 3 domain scores, which are sums of the scores of the following consideration of questions ([Appendix B](#)): disease domain (questions 1 to 3), mood/emotional distress domain (questions 4 to 6), and social functioning domain (questions 7 to 10). Change from baseline in itch-related quality of life at each of the post baseline weeks of the treatment period with respect to each of the 3 domains of the Skindex-10 Scale will be calculated. Treatment differences with respect to each domain will be evaluated using a model similar to the MMRM fitted for the analysis of the change from baseline in the total score of the Skindex-10 Scale.
- Change from baseline in itch-related quality of life at week 12 of the treatment period and at each of the remaining weeks of the treatment period with respect to each of the domains of 5-D Itch scale. Treatment differences with respect to each domain will be evaluated using a model similar to the MMRM fitted for the analysis of the change from baseline in the total score of the 5-D Itch Scale. The domain score derivation will be considered as detailed in the [Appendix C](#).

Listings will be provided for the variables used in the additional efficacy endpoints (which are not mentioned in the primary or secondary analysis).

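### The SAP formula for the 5-D Itch total counts duration twice and leaves out direction, contradicting the five-domain rule in its own Appendix C

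*SAP*

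**What the plan says.** The scoring rule for the 5-D Itch total stands in two places in the SAP, and both have the same terms.

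- Appendix C: "Total 5-D Itch score = duration score (single item) + degree score (single item) + duration score (single item) + maximum (4 disability items", followed by the distribution category.
- Section 7.1: "Total 5-D Itch score = duration score (single item) + degree score (single item) + duration score (single item) + maximum disability", again followed by the distribution category.

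The prose of Appendix C, just above its formula, gives a different rule: "The scores of each of the five domains are achieved separately and then summed together to obtain a total 5-D Itch score". It also lists the single-item domains: "Single-item domain scores (duration, degree and direction) are equal to the value indicated below the response choice". Protocol 6.5.1.3 agrees with that prose: "The 5 dimensions of itch assessed are degree, duration, direction, disability, and distribution". The instrument reproduced in both documents has a separate direction item with five response choices.

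The total defines a key secondary endpoint in SAP 8.6.3: "Change from baseline in itch-related quality of life at the end of Week 12, as assessed by the total 5-D Itch scale score". That section sends the reader to Appendix C for the derivation. SAP section 9, which lists the departures from the protocol, mentions no change in 5-D scoring.

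**The concern.** The SAP gives two incompatible rules for one score, and no program can satisfy both. SAP section 1 says that the document supplies the data derivations and that deviations must be justified in the study report. Protocol 8.1 gives the SAP primacy over the protocol where analyses differ. So the protocol's list of dimensions does not clearly override the formula, and the explicit equation is what a programmer would most naturally code.

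If it was coded literally, the following use a mis-scored total:

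- the Week 12 key secondary analysis (MMRM with multiple imputation);
- the pooled-dose comparison, the dose-trend test and the renal-status results;
- the other visits (SAP 8.6.4) and the interim summary (SAP 8.9.2.4);
- the model for itch rated as not present or completely resolved, which adjusts for "baseline 5-D Itch Total Score and renal disease status".

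Not affected are the primary NRS endpoint, Skindex-10, the NRS responder endpoint, the sample-size re-estimation rule and the separate 5-D domain analyses. For the last of these SAP 8.6.4 says "The domain score derivation will be considered as detailed in the" Appendix C, whose domain rules are sound.

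**Working it through.** **Inputs.** Each domain is scored 1 to 5 (SAP Appendix C). The stated range of the total is 5 to 25 (SAP 7.1 and Appendix C). Lower is better, and change is Week 12 minus baseline.

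**The two rules**

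- As written: 2 × duration + degree + disability + distribution
- Five-domain: duration + degree + direction + disability + distribution

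**Reproducing the stated range.** As written, the minimum is 2 × 1 + 1 + 1 + 1 = 5 and the maximum is 2 × 5 + 5 + 5 + 5 = 25. The five-domain rule gives 5 × 1 = 5 and 5 × 5 = 25. Both match the SAP, so the range cannot show which rule was used.

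**Error at one assessment.** As written minus five-domain = duration − direction.

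- The totals agree only when the two items are equal: 5 of 25 pairs. They differ in 20.
- The bounds are 1 − 5 = −4 and 5 − 1 = +4. The lower one is a plausible answer (under 6 hours a day and getting worse). The upper one needs itching all day that is also completely resolved.

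**Error in a change score.** Change in duration − change in direction. A positive value means that improvement is understated.

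- The change scores agree when duration − direction is the same at both visits. A difference of k arises in 5 − |k| pairs, so the count is 25 + 2 × (16 + 9 + 4 + 1) = 85 of 625 combinations, and 540 differ. These are counts of possible responses, not shares of patients.
- The bounds are −8 and +8, and each needs the contradictory pair at one visit.

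**Worked case.** Baseline direction is 'Unchanged' (4). At Week 12 direction is 'Completely resolved' (1) and duration is 1. Change on these two items:

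| Baseline duration | Five-domain change | Change as written | Error |
|---|---|---|---|
| 1 | −3 | 0 | +3 |
| 2 | −4 | −2 | +2 |
| 3 | −5 | −4 | +1 |
| 4 | −6 | −6 | 0 |
| 5 | −7 | −8 | −1 |

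For any patient whose direction improves from 4 and whose duration does not rise, the error lies between −3 and +3. The low end is duration 5 to 1 with direction 4 to 3: −4 − (−1) = −3. The high end is duration unchanged with direction 4 to 1: 0 − (−3) = +3.

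**A milder hypothetical patient.** Baseline duration 3, degree 4, direction 4, disability 4, distribution 3 gives 17 as written and 18 by the five-domain rule. With every domain at 2 at Week 12, both totals are 10. The change is −7 as written and −8 by the five-domain rule.

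**Treatment contrast.** With complete data, the raw active-minus-placebo difference in mean change shifts by the duration effect minus the direction effect. The documents give neither effect. Assuming 0 to −0.5 point on duration and 0 to −0.75 on direction, the shift runs from −0.5 − 0 = −0.5 to 0 − (−0.75) = +0.75 point. The model-based estimate would differ somewhat, because the baseline covariate changes as well.

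**The case against.** The strongest reply is that the intended rule is obvious. The formula has three single-item terms, the prose names the three single-item domains, and the third term simply has the wrong name. On this reading it is a one-word slip copied to a second place, and harm needs a programmer to follow the formula against the paragraph above it. That is probably how the error arose, and the documents do not show that any score was actually mis-calculated. But the slip is in the operative equation, in both places where an analyst would look for it.

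A second reply is that little depends on this endpoint. Under SAP 8.6.2 and section 9 effectiveness is judged on the primary analysis, and no alpha passes through the 5-D total, since there is no multiplicity adjustment. This is true and limits the consequence. It does not make a key secondary endpoint with two scoring rules acceptable.

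A third reply concerns size. The assumed direction effect is one-sided. The item asks about change against the previous month, so patients who improved early and then held steady may answer 'Unchanged' at Week 12. If placebo patients were still improving then, the direction effect could be positive and the shift could fall below −0.5. That point stands: the range is illustrative, not a bound. The documents also give no standard deviation or meaningful-change threshold for the 5-D total against which to judge it.

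Finally, the SAP already requires domain scores and listings of the collected 5-D scores, so the error can be found from existing output. That is so, provided someone compares the domain sum with the total; the SAP does not ask for this.

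**Conclusion.** The concern holds. The formula in SAP 7.1 and Appendix C is wrong as written: it contradicts Appendix C's own scoring rule and the protocol's list of dimensions, and no change of scoring is announced. That the text conflicts is certain. Whether scores were affected depends on the code, which the documents do not show.

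If the formula was followed, every assessment on which duration and direction differ is mis-scored by their difference, at most 4 points, on a scale that spans 20 points (25 − 5). The net effect on the treatment comparison could go either way. The −0.5 to +0.75 range rests wholly on assumed item effects. The correction should be made before the 5-D total is reported, because a key secondary endpoint needs a single scoring rule and range checks will not reveal a wrong one.

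**What to change.** 1. In SAP 7.1 and Appendix C, replace the second duration term with the direction score (single item).
2. Confirm that the derivation program, including the one used for any interim output, sums the five domains.
3. Add a programming check that the five domain scores add up to the total at every assessment. The domain scores are needed anyway for the analyses in SAP 8.6.4.
4. If the literal formula was used, rerun all outputs that rest on the 5-D total, including the model that uses the baseline total as a covariate.

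The cost is one word in two places, a code check and possibly a rerun. No new data are needed.

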Appendix D: Patient Global Impression of Change

This is a representation of the content of the instrument to be used. Please refer to the Study Reference Manual for the instrument to be administered to patients and instructions.

Since the start of the study, my itch is:

1. **Very much improved**
2. **Much improved**
3. **Minimally improved**
4. **Not changed**
5. **Minimally worse**
6. **Much worse**
7. **Very much worse**

Date Completed:									
  D	  M	  M	  M	 2	 0	  Y	 Y	 Y	 Y

Time:	
  :	  
 AM	 PM

SUBJECT INITIALS		
  	First	Middle
  	Last	

Statistical Analysis Plan (SAP)

Appendix E: Patient Global Impression of Change

This is a representation of the content of the instrument to be used. Please refer to the Study Reference Manual for the instrument to be administered to patients and instructions.

Please indicate the severity of the **WORST ITCHING** you experienced over the past 24 hours by marking the box with the category that best describes it.

- None**
- Mild**
- Moderate**
- Severe**
- Very severe**

Date Completed:									
									
D	D	M	M	M	2	0			Y
Y Y Y Y									
Time:									
		:							
 AM		 PM							
SUBJECT INITIALS First Middle Last									
									

Statistical Analysis Plan (SAP)

The image consists of a series of thick, black horizontal bars of varying lengths and positions, set against a white background. The bars are arranged in a stepped, ladder-like pattern that is symmetrical across the center. The lengths of the bars decrease as they move from left to right. Some bars are positioned higher than others, creating a sense of depth. The bars are composed of multiple horizontal segments, giving them a pixelated or digital appearance. The overall effect is abstract and geometric.

Statistical Analysis Plan (SAP)

[REDACTED]

[REDACTED]

[REDACTED]

[REDACTED]

[REDACTED]

[REDACTED]

Statistical Analysis Plan (SAP)

[figure not shown]

A high-contrast, black and white image showing a complex, abstract shape composed of numerous black pixels on a white background. The shape is roughly triangular in orientation, with a jagged, stepped profile. It features several horizontal bars of varying lengths at the top and a large, irregularly shaped block on the left side. The overall appearance is digital and geometric.

Statistical Analysis Plan (SAP)

Appendix

Statistical Analysis Plan (SAP)

[REDACTED]

[REDACTED]

[REDACTED]

[REDACTED]

[REDACTED]

[REDACTED]

[REDACTED]

[REDACTED]

Statistical Analysis Plan (SAP)

The image consists of a series of horizontal black bars of varying lengths and positions, set against a white background. The bars are irregular in shape, with some having sharp ends and others being more rounded. They are positioned in a way that suggests they are redacting text or obscuring specific information. The overall effect is one of a heavily processed or heavily redacted document.

Statistical Analysis Plan (SAP)

A large black rectangular redaction box covers the majority of the page content, starting below the header and ending above the footer. The redaction is irregular, with some white space visible at the top and bottom edges.
